- While performing this practice, participants will be instructed to take a 15- 20 seconds break if feeling dizzy.
- Participants will be instructed to not stress the body or overdo the exercise beyond capacity.

Step 3: Participants will be instructed to close mouth, inhale fully and simply sit for 30-60 seconds in full inspiration. After 30-60 seconds, exhale with a constriction in pit of throat and relax.

Upon completion of breathing techniques, participants will be instructed to sit in meditation for 2 minutes or longer with eyes closed. Participants will be instructed to not judge their thoughts, to be an observer, and just let their thoughts pass by without focusing on anything.

If you feel short of breath, or unable to perform the practices please do not continue with the practice. Please contact your doctor for further medical attention and notify the study team.

Video link of the practice is as follows-

<https://www.youtube.com/watch?v=IP1Y1bk1YgU>

Measures: The following measures will be completed during the course of 4 weeks through a REDCap data base

Adherence: Participants will keep a record of when they practiced each day to report in the survey how many times a day and how many days a week participant practiced for each of the 4 weeks.

Breath holding time: At baseline and the end of each week, participants will count how many seconds they can hold their breath at one time. Participants will be asked to use the stopwatch on their smartphones to time breath holding. They will first empty their lungs as much as possible with an extended exhale pulling in their diaphragm using abdominal breathing. They will then inhale fully extending their diaphragm out and start timing how many seconds they can hold their breath. After a 2-

minute rest period they will repeat and record the second number. They will record both numbers at end of each week and report the results in the survey.

Meditation perception questionnaire (including perception of usefulness): At the end of each week, participants will be asked 7 questions regarding their perception of practice such as feeling more peaceful, hopeful, relaxed, in more control of life, if they noticed improvement in their breathing, if they found the practice useful, and if they will continue to engage in the practice. We used this questionnaire in our previously published meditation study (14) and added 2 questions.

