This study is being conducted with HCWs who are currently at the forefront of pandemic management. Due to overwhelming response and willingness to participate in the study, we decide to increase our accrual from 50 to 100. The increased sample size will allow for increased precision or power in assessing both the primary and secondary objectives. When the sample size is 100, a two-sided 95% confidence interval (CI) for the proportion of perception of the intervention as usual using the large sample normal approximation will extend 0.098 from the observed proportion for an expected proportion of 0.500. In addition, a sample size of 100 will have 80% power to detect a difference in mean of 0.283 standard deviation (SD) unit between baseline and a time point after baseline, using a paired t-test with a 0.050 two-sided significance level. Attrition is unlikely in our study setting given that the participants are HCWs during the pandemic of COVID-19. However, in the unlikely case of a 10% attrition, a resulting sample size of 90 ($=100*0.9$) will have 80% power to detect a difference in mean of 0.299 SD unit between baseline and a time point after baseline, using a paired t-test with a 0.050 two-sided significance level. In both scenarios, the detectable effect size is considered medium.

Data Analysis:

Baseline characteristics of participants will be recorded. Continuous data will be presented as means \pm standard deviation or median (interquartile range) depending on the distribution of the data and assessed with a parametric paired t-test or non-parametric Wilcoxon signed rank test for the changes between time points, as appropriate. Normality will be assessed with the Shapiro-Wilk test. Categorical data will be presented as frequencies and percentages and assessed with a chi-square or Fisher's exact test, as appropriate. SPSS will be used for all analyses with two-sided p-values < 0.05 considered statistically significant.

Feasibility will be defined as recruitment of 50 participants to the study within 2 months and acceptance of the study defined as more than 50% of participants perceive the intervention as useful. Adherence will be assessed using data from how often participants complete their breathing techniques. This will be reported as the percentages of completed activities out of the total required per protocol.

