Exploratory regression analysis for adherence to protocol for various outcomes is also planned. Protocol adherence for the study has been defined as participation in the intervention for more than 3 days in a week. Participant perception will be measured using a survey. Continuous and dichotomous data will be reported and assessed in a similar fashion as above.

Given the continuous nature of the scale, differences between scores will be assessed with a paired parametric or non-parametric t-test. In the absence of randomization, unadjusted and adjusted linear regression will be utilized in order to account for differences that persist. Our primary analyses will be assessed using intention-to-treat principles. In order to assess whether there are differences between baseline and at various intervals, we will employ the use of paired t-tests as appropriate.

For the analyses of the changes of variables over time (starting from baseline), we will also use linear mixed-effects models.

Risks:

The risk to the subject is minimal as intervention involves breathing techniques based on yoga and meditation.

Potential physical risks of the study interventions:

The interventions offered in this study are simple and only involves meditation and breathing practices. Participants may feel light headed for a short period of time. As such, there are no physical risks expected with these interventions. Similarly, by assessing stress or well-being measures, we do not anticipate any risk of physical harm to any of the research subjects. Hand held spirometer is easy to use. The twenty participants selected for this extra measure will be nurses, physicians or respiratory therapists who report knowing how to use the spirometer.

Potential psychological risks:

It is possible that there could be psychological or emotional risk to subjects in this study if they were to become aware of their performance in assessments and more so than they would be if they were not participating in the study. Subjects will not be given the scores of their assessments, but if they were to become aware of a decline in their performance this could be stressful or disconcerting to the subject. For additional counseling regarding any psychological or emotional distress stemming from this, participants will be referred to Employee Assistance Program (EAP) at the request of the subject.

Data security and privacy:

Risk of breach of confidentiality:

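### Does naming only chi-square or Fisher's exact test for categorical data mishandle perception items that the same participants answer every week?

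*Combined protocol and SAP*

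**What the plan says.** All the relevant text is in the combined protocol and SAP.

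- **Data Analysis, continuous data:** these are "assessed with a parametric paired t-test or non-parametric Wilcoxon signed rank test for the changes between time points, as appropriate".
- **Data Analysis, categorical data:** "Categorical data will be presented as frequencies and percentages and assessed with a chi-square" or Fisher's exact test, whichever suits. This sentence does not mention time points.
- **Data Analysis, participant perception:** after saying that perception is measured by survey, the plan adds: "Continuous and dichotomous data will be reported and assessed in a similar fashion as above".
- **Data Analysis, score differences:** the next sentence refers to a scale of continuous nature and assigns paired parametric or non-parametric tests to differences between scores. It does not say which scale.
- **Data Analysis, repeated measures:** "For the analyses of the changes of variables over time (starting from baseline), we will also use linear mixed-effects models".
- **Measures, meditation perception questionnaire:** "At the end of each week, participants will be asked 7 questions regarding their perception of practice". No response format is given, and no baseline administration is listed.
- **Aims and Data Analysis, acceptance:** "acceptance of the study defined as more than 50% of participants perceive the intervention as useful".

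**The concern.** Each participant can answer the perception items up to four times. Data Analysis sends dichotomous perception data back to the methods listed earlier, and the only categorical methods there assume independent observations. Continuous outcomes get a paired test in the same paragraph, so the omission looks like an oversight.

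The linear mixed-effects model does not clearly fill the gap. It starts from baseline, which these items lack, and a linear model is not designed for yes/no answers.

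The stake would be a week-to-week comparison of perception, and the harm would depend on the table used:

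- **Weekly proportions.** Chi-square treats the weeks as different people. With positive within-person correlation it is conservative and may miss a real shift.
- **One week cross-classified against another.** Chi-square tests whether the answers are associated, so a small p-value shows agreement and not change.

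**Working it through.** **1. The plan's own figures.** None involves a categorical comparison over time.

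- Confidence-interval half-width, n = 100, proportion 0.50: 1.96 × √(0.5 × 0.5 / 100) = 1.96 × 0.05 = 0.098, as stated.
- Paired t-test, n = 100, 0.283 SD: noncentrality 0.283 × √100 = 2.83 on 99 df gives power 0.800, as stated.
- Paired t-test, n = 90, 0.299 SD: noncentrality 0.299 × √90 = 2.84 on 89 df gives power 0.801, as stated.

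**2. Which objectives need a paired categorical test?**

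| Objective (Aims) | Quantity | Paired categorical test needed? |
|---|---|---|
| Recruitment | Count within 2 months | No |
| Acceptance | One proportion against 50% | No |
| Adherence | One proportion at week 1 | No |
| Resilience, stress, COVID-19 impact | Change in score, day 0 to day 28 | No; paired tests named |
| Breath holding over time | Seconds, weekly | No; paired tests and mixed model named |
| Breath holding by adherence | Seconds, different people | No |

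The modified GSE is completed once, so it raises no pairing question. Perception is the one questionnaire where the question arises, and no objective is a change in perception.

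**3. Size of the effect if two weeks were compared anyway.** The documents give neither the within-person correlation (phi) nor any weekly shift. Both are assumed here, as is a yes/no format.

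The variance of the difference between two paired proportions is [p₁q₁ + p₂q₂ − 2·phi·√(p₁q₁p₂q₂)] / n. Chi-square on the weekly proportions sets phi to 0. At 50% in both weeks the true variance is (1 − phi) times the one used, so the approximate error rate is 2 × [1 − Φ(1.96 / √(1 − phi))]. At phi = 0.33 this gives 1.96 / √0.67 = 2.39 and an error rate of about 1.7%. Simulation, which allows for discreteness, gives 1.9%.

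Simulated results, n = 100, 40,000 trials per setting, correlated binary pairs from a latent normal, two-sided 0.05:

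| Phi at 50/50 | 0 | 0.19 | 0.33 | 0.49 | 0.65 |
|---|---|---|---|---|---|
| Chi-square, no change: error rate | 5.7% | 3.4% | 1.9% | 0.7% | 0.15% |
| McNemar, no change: error rate | 5.1% | 5.0% | 5.0% | 5.3% | 5.1% |
| Chi-square, 50% to 62%: power | 42% | 40% | 40% | 38% | 36% |
| McNemar, 50% to 62%: power | 40% | 47% | 55% | 67% | 81% |
| Exact McNemar, 50% to 62%: power | 35% | 41% | 47% | 58% | 74% |
| Chi-square on the cross-table, no change: p < 0.05 | 5% | 51% | 93% | 99.9% | 100% |

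On weekly proportions, correlation brings lost power and not extra false positives. The last row is a test of a different hypothesis, and nothing in the plan calls for that layout.

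**4. Four weeks.** Assumed proportions are 50, 54, 58 and 62%, n = 100, with latent correlation 0 / 0.3 / 0.5 / 0.7 / 0.85.

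- Complete answers: chi-square 29 / 24 / 20 / 15 / 9%; Cochran's Q 29 / 35 / 42 / 55 / 70%.
- 10% of answers missing at random each week (assumed): complete responders number 100 × 0.9⁴ ≈ 66. Cochran's Q falls to 21 / 24 / 29 / 36 / 49%, against 28 / 22 / 19 / 14 / 9% for chi-square.
- 20% missing each week (assumed): 100 × 0.8⁴ ≈ 41 remain. Cochran's Q is below chi-square at latent correlations 0 and 0.3, and level at 0.5 (18% each).

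The better paired method therefore depends on how complete the weekly answers are, which is not known in advance.

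**The case for a change.** The strongest case for a change is textual. Dichotomous perception data are to be assessed as well as reported, the only methods they can inherit are chi-square and Fisher's exact test, and the qualifier there covers a choice between those two, neither of which is paired. In a one-arm study with weekly items, comparing weeks is a natural thing to do, and one sentence would settle the matter at no cost in data.

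Much of this stands. No paired method for binary data is named, and the linear mixed model is a poor substitute. The sentence on continuous scales could give scored perception items a paired test, but its referent is unclear and it would not reach true yes/no answers.

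What does not stand is the step from an unnamed method to a wrong analysis. In "non-parametric Wilcoxon signed rank test for the changes between time points, as appropriate" the reference to time points belongs to the continuous sentence, and the categorical sentence has no counterpart. The harm needs two things that the documents do not state: that the items are yes/no, and that weeks will be compared. If weekly perception is simply described, the extra sentence would only record that intention.

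**Conclusion.** No change is needed. The wording has a gap of the kind that analysts fill sensibly: an analyst who chose to compare yes/no answers between weeks would use a paired or repeated-measures method, and the plan does not direct otherwise. Followed as written, the plan gives no wrong result for any stated objective, and chi-square or Fisher's exact test remains sound between different people.

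If chi-square were misapplied to two weekly proportions, the cost under the assumed 50% to 62% shift would run from none at zero correlation to 45 percentage points of power relative to McNemar at phi 0.65 (81 − 36). It would fall on an unplanned secondary or exploratory comparison. The cross-table misreading could be more misleading, but it needs a layout that the plan never proposes. These sizes rest on assumed correlations and shifts, a yes/no format and, except where stated, complete answers. The conclusion itself rests on the text: no objective compares perception across weeks.

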Breathing Techniques and Meditation for Health Care Workers During COVID-19

PI: [name] MD

Collaborators: [name], [name], [name] MD [name] MD [name] MS

Senior Authors: [name] PhD [name] MD

Introduction:

Pranayama is a term used to describe breathing techniques that are an integral part of yoga practice. Numerous studies have shown the benefit of yoga in healthy volunteers and cancer patients. (1,2, 3,4, 5, 6, 7) The benefits range from decreasing inflammation as evidenced by reduction of inflammatory cytokines to improvement in immune system as evidence by increasing non-killer/NK cells. (8) In our own studies, we have shown evidence of yoga improving chemotherapy-related cognitive dysfunction and reducing anxiety in cancer patients and caregivers in addition to improving both their quality of life. (1,9) The pandemic COVID-19 has created chaos and distress for the entire world, especially for healthcare workers. Here we suggest a series of 3-minutes breathing or pranayama practices followed by 2 minutes of meditation – overall 5 minutes to complete. The purpose of this study is to determine the effects of web-based breathing techniques and meditation on lung health and building resilience among health care workers dealing with the COVID-19 pandemic.

AIMS:

Primary Outcome:

To demonstrate the feasibility of a short pranayama or breathing techniques and meditation during Covid-19 pandemic. Feasibility will be defined as recruitment of 50 participants to the study within 2 months and acceptance of the study defined as more than 50% of participants perceive the intervention as useful.

Secondary Outcomes:

1. To determine the adherence to the practice assessed as at least 50% of participants implement the intervention for 3 or more times in a week by the end of week 1/day 7 (+ 3 days)
2. To determine the change in resilience, perceived stress and psychological impact from day 0 to day 28 as measured by the Brief Resilient Coping Scale (BRCS), Perceived Stress Scale (PSS4), and COVID-19 Stress among health care workers questionnaire
3. To determine the changes in breath holding time measured weekly for 4 weeks
4. To determine the differences in breath holding time between those who are adherent and those who are not adherent to the practice

Background/Rationale:

Current COVID-19 climate and stress on health care:

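### Does the acceptance criterion need a named week and a rule for missing usefulness answers?

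*Combined protocol and SAP*

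**What the plan says.** AIMS (Primary Outcome) and Statistical Considerations (Data Analysis) define feasibility as 50 recruits within 2 months together with "acceptance of the study defined as more than 50% of participants perceive the intervention as useful". The question sits in the Meditation perception questionnaire under Measures: "At the end of each week, participants will be asked 7 questions regarding their perception of practice", and one of these asks "if they found the practice useful, and if they will continue to engage in the practice". Study Procedures places the follow-up surveys at 1, 2, 3 and 4 weeks, so each participant can give four usefulness answers.

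On the denominator, Data Analysis says "Our primary analyses will be assessed using intention-to-treat principles". The Sample Size Justification gives the confidence interval for this same proportion at a sample size of 100. Its attrition scenario, "in the unlikely case of a 10% attrition, a resulting sample size of 90", is applied to the paired t-test and not to this proportion.

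Other outcomes have named times. Adherence is judged at the end of week 1 with a 3-day window. The scale scores, including "perceived stress and psychological impact from day 0 to day 28", compare baseline with the end of the study. The Global Symptom Evaluation is completed at week 4 or on removal.

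**The concern.** A pass/fail primary criterion normally has one deciding measurement and a stated treatment of missing values. Here there are four candidate answers per person and no stated choice. Because the plan uses both week 1 and week 4 elsewhere, either could be defended for acceptance. A participant who stops returning surveys could be dropped from the count, scored as not finding the practice useful, or represented by an earlier answer.

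The study has a single arm and the team can see the answers as they arrive, so the week and the rule could in principle be chosen after the result is known. If acceptance fell close to 50%, that choice could decide whether the study is declared feasible.

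**Working it through.** **Inputs from the plan.** Planned enrolment 100; threshold more than 50%; expected proportion 0.500; stated 95% half-width 0.098; attrition scenario 10%, leaving 90. The true usefulness rates and between-week correlations below are assumptions.

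**Reproducing the plan's figure.** Half-width = 1.96 × √(0.5 × 0.5 / 100) = 0.098, as stated. With 90 answers it would be 1.96 × √(0.25 / 90) = 0.103.

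**Choice of week, 100 answers each week.** A pass needs 51 or more favourable answers. At a true 45% in every week, the exact binomial P(X ≥ 51) = 0.135 for any single week. In a simulation of correlated weekly answers (latent correlation 0.9 down to 0.5), the week-1 and week-4 verdicts differed with probability 0.133 to 0.196. Then:

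- P(at least one of weeks 1 and 4 passes) = (0.135 + 0.135 + P(verdicts differ)) / 2
- lower end: (0.270 + 0.133) / 2 = 0.20
- upper end: (0.270 + 0.196) / 2 = 0.23

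Free choice among all four weeks gives 0.28 to 0.37, but weeks 2 and 3 have no special standing in the plan. At a true 60%, the four weeks fail to agree with probability 0.068 to 0.093; at 65%, with 0.004 to 0.006.

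**Missing answers, 100 enrolled and 10 without an answer.** Counting responders only, a pass needs 46 of 90 (51.1%). Counting all enrolled with a missing answer as not useful, it needs 51 of 100, which is 51/90 = 56.7% of responders. The two rules disagree when 46 to 50 answers are favourable. Exact binomial results on 90 answers, with answers missing at random:

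| True rate among responders | Responders only passes | All enrolled passes | Rules disagree |
|---|---|---|---|
| 45% | 0.145 | 0.017 | 0.127 |
| 55% | 0.802 | 0.417 | 0.384 |
| 60% | 0.965 | 0.775 | 0.190 |
| 65% | 0.998 | 0.960 | 0.038 |
| 70% | 1.000 | 0.997 | 0.003 |

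**What the plan's wording gives.** The criterion counts participants who perceive the practice as useful. Under intention-to-treat the denominator is those enrolled, and a person who never reported usefulness is not in the numerator. That is the all-enrolled column. Its errors run toward failing to declare acceptance: at a true 45% it passes less often (0.017) than a complete count would (0.135).

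**What any written rule would cost.** Week 4 with missing scored as not useful passes at a true 60% with 0.775 at 10% missing and 0.286 at 20% missing, against 0.973 with none missing. The last available answer softens this: at 20% missing at week 4 it passes with 0.775 if half of those missing had answered earlier, and 0.973 if all had. However, it mixes one to four weeks of practice and credits an early favourable answer from someone who then stopped.

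**The case for a change.** The strongest case for a change is that this is a primary criterion, the plan fixes times for other outcomes but not for this one, and a few sentences would close the gap without new data. Intention-to-treat names a population but does not score a non-response. The precision is worked out at an expected proportion equal to the threshold, so results near 50% are within what the plan contemplates. Larger effects can also be shown. If usefulness drifted from 55% in week 1 to 45% in week 4, week 1 would pass with 0.817 and week 4 with 0.135. With 20% non-response, all of it unfavourable, and 45% of all enrolled favourable, a responder-only count would pass with 0.845.

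The omission itself stands, and so does the arithmetic. The large effects carry less weight. The drift is set to straddle the threshold, and the second case doubles the plan's attrition, makes every non-responder negative, and uses a responder-only count that the wording does not support. An expected proportion of 0.500 is also the value that makes the interval widest, so it need not be a forecast.

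**Conclusion.** The plan leaves out a detail; it does not state a rule that gives a wrong answer. Its wording already points to all enrolled as the denominator, and an analyst who reports week 4 on that basis reaches a sound conclusion. The remaining freedom matters only near 50%. At an assumed true 45%, choosing between weeks 1 and 4 raises the chance of a pass from 0.135 to about 0.20 to 0.23. At an assumed 65% with 10% missing at random, the two missing-answer rules disagree with probability 0.038, and the four weeks (complete answers) with probability below 0.01.

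The setting limits the harm further. This is a single-arm pilot with a descriptive threshold, and the planned interval of about ±0.098 would show a result near 50% as uncertain under any rule. The Global Symptom Evaluation gives a separate reading of acceptability at week 4 or on removal. Because each explicit rule has a measurable cost and none is clearly better, the choice is a fair trade-off for the team and no change to the plan is called for. This rests on attrition near the plan's 10%; with much heavier non-response the missing-answer rule would matter over a wider range of true rates.

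### Does breath holding time need one named reading, one main model and one main week before the analysis starts?

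*Combined protocol and SAP*

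**What the plan says.** Secondary Outcomes, item 3, sets the aim: "To determine the changes in breath holding time measured weekly for 4 weeks". Under Measures, Breath holding time, the schedule is "At baseline and the end of each week, participants will count how many seconds they can hold their breath at one time". The hold is repeated after a two-minute rest, and "They will record both numbers at end of each week and report the results in the survey".

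Data Analysis sets one threshold throughout: "SPSS will be used for all analyses with two-sided p-values < 0.05 considered statistically significant". Changes are tested with a paired t-test or a Wilcoxon signed rank test, and "Normality will be assessed with the Shapiro-Wilk test". The same section then says "In order to assess whether there are differences between baseline and at various intervals, we will employ the use of paired t-tests as appropriate" and "For the analyses of the changes of variables over time (starting from baseline), we will also use linear mixed-effects models".

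Sample Size Justification gives, for 100 participants, "80% power to detect a difference in mean of 0.283 standard deviation (SD) unit between baseline and a time point after baseline", and 0.299 SD for 90 participants. It does not name the time point.

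The sentence on various intervals does not name breath holding. That it applies is an inference: PSS-4, BRCS and the COVID-19 stress measure are taken only at baseline and at the end, and the weekly perception questionnaire has no stated baseline. A spirometer measure in twenty participants is mentioned under Risks, without a schedule.

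**The concern.** Baseline plus four weekly follow-ups gives four comparisons with baseline. Each can be made with the first, the better or the mean of two readings, and with a paired test or a mixed model. The plan ranks none of these, and any p-value below 0.05 counts. An analyst could, without breaking the plan, report whichever combination is significant. With no control group, a pre-stated analysis is one of the few protections against that. The power statement covers a single comparison, so it does not describe four weekly tests. The Shapiro-Wilk step could also mean that different weeks are tested with different methods.

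At stake is how far a reader can trust a claim that breath holding changed. This is the scheduled measure closest to the lung-health purpose in the Introduction.

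**Working it through.** **1. The plan's own figures.** Paired t-test, two-sided 0.05, effect d in SDs of the change, noncentrality d√n, n − 1 degrees of freedom.
- n = 100: 0.283 × 10 = 2.830, critical value 1.984, power 0.800. Solving for 80% gives d = 0.2829.
- n = 90: 0.299 × 9.487 = 2.837, critical value 1.987, power 0.801. Solving gives d = 0.2985.

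Both figures reproduce, for one comparison.

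**2. Four weekly tests.** The documents give no correlations, so these are assumed.
- Independent tests: 1 − 0.95⁴ = 0.185. Bonferroni bound: 4 × 0.05 = 0.20.
- Shared baseline, occasions equally correlated at ρ: each change has variance 2σ²(1 − ρ), and two changes have covariance σ²(1 − ρ), so they correlate 0.5 whatever ρ is. Simulated chance of at least one p < 0.05 at n = 100: 0.154-0.160.
- Correlation decaying by week, AR(1) 0.5/0.7/0.8/0.9: 0.146/0.138/0.138/0.132.
- Week 4 alone: 0.048-0.053.

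Bonferroni over four weeks (0.0125 each) would raise the detectable difference to 0.339 SD (n = 100) or 0.358 SD (n = 90). Power at the stated effects would fall to 61%.

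**3. Two readings.** Assumed correlation 0.5 or 0.7 between occasions and 0.8-0.95 within an occasion. If first, best and mean are all tried, the chance of at least one significant result is 0.065-0.092 at week 4 and 0.196-0.274 over four weeks. Any one definition used consistently gives 0.047-0.053 at week 4. The choice of definition therefore does not affect error; only switching between definitions does.

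**4. Shapiro-Wilk switch.** This step adds little.
- If change scores are skewed but forced to mean zero (gamma, skewness 1), the switch rejects 13.6% in one week, against 5.2% for the t-test. But that is not a state of no change: the median change is −0.16 SD and 57% of participants decline.
- If nothing changes and baseline and follow-up are exchangeable, their difference is symmetric however skewed the times are, and the Wilcoxon test is valid. With lognormal times of skewness 0.9/1.8/3.7 (log-scale correlation 0.7, n = 100), the switch rejects about 5% in each case.

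**5. Would one mixed-model contrast settle it?** Not by itself; the covariance structure matters. With complete data, a random-intercept model estimates the variance of the week-4 contrast as proportional to 1 − r̄, where r̄ is the mean of the ten pairwise correlations. The true variance is proportional to 1 − ρ⁴ under AR(1). With r̄ = (4ρ + 3ρ² + 2ρ³ + ρ⁴)/10, the error rate is 2[1 − Φ(1.96/√ratio)]:

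| ρ | r̄ | (1 − ρ⁴)/(1 − r̄) | error at week 4 |
|---|---|---|---|
| 0.5 | 0.306 | 0.938/0.694 = 1.351 | 9.2% |
| 0.7 | 0.520 | 0.760/0.480 = 1.582 | 11.9% |
| 0.8 | 0.655 | 0.590/0.345 = 1.713 | 13.4% |
| 0.9 | 0.814 | 0.344/0.186 = 1.853 | 15.0% |

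So one contrast from a loosely specified mixed model can carry about as much error as four paired tests. An unstructured covariance avoids this: with complete data its week-4 contrast and standard error equal those of the paired t-test.

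**6. Week 4 against an overall test of week.** Detectable differences at 80% power, n = 100, complete data (equal correlation 0.7 / AR 0.8 / AR 0.9):
- Steady rise, size at week 4: overall test 0.317/0.354/0.354 SD; week-4 test 0.283 SD.
- Immediate constant change: overall test 0.280/0.204/0.190 SD; week-4 test 0.283 SD.

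The week-4 test is better for a steady rise, and the overall test for an early change that persists. The documents do not say which pattern is expected.

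**The case for a change.** The case for amending the plan is fair. The plan attaches a significance threshold and a power claim to changes between time points, so it cannot be read as purely descriptive. Day 28 is named for the questionnaires in secondary outcome 2 but not for breath holding, so week 4 cannot be assumed. A mixed model selects neither a reading nor a contrast. The remedy would cost only a few words, since the model is already planned and both readings are already collected.

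Most of this stands as description: no reading, week or ranking is stated, and reading four tests at 0.05 roughly triples the nominal error rate. What does not follow is that the plan must change. The text partly separates the two methods: mixed models are assigned to change over time from baseline, which closely matches a weekly objective, and paired tests to comparisons of individual intervals with baseline. Fixing on week 4 would narrow that objective, could miss a change that peaks earlier, and would lose power where an early change persists. Calling one contrast confirmatory would also give breath holding a status the protocol does not claim for it.

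**Conclusion.** The omission is genuine, but it is ordinary missing detail in a brief plan. An analyst would use one reading rule on every occasion, for instance the mean, show all four weeks, and treat the paired and mixed-model results as two views of the same data. Any consistent reading rule keeps a single test at about 5%.

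The excess error, about 13-16% for at least one of four weekly tests, rests on assumed correlations and n = 100. It applies only if any single significant week is taken as the finding. Naming one contrast would remove it, but which contrast is a trade-off: 0.283 SD against 0.317-0.354 SD for a steady rise, and 0.283 SD against 0.190-0.280 SD for a constant change.

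Breath holding is a secondary outcome in a single-arm pilot. Without a control group, a significant week could not be attributed to the practice whichever test produced it. The primary conclusion rests on recruiting 50 participants within two months and more than half finding the intervention useful, and nothing here alters it. No change is needed.
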